
Missing data. Analysis of our primary aim will be based on intent-to-treat principles using imputation for missing data. If the proportion of participants lost to follow-up differs by treatment we will determine if there are differences in demographic characteristics (sex, age, baseline weight, $p < 0.05$) between completers and those lost to follow-up. If missing data are related to treatment and/or demographic characteristics, we will use model based multiple imputation; otherwise, we will use traditional multiple imputation ($k=5$). Statistical procedures will be performed using SAS version 9.4 or higher.

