Overview of approach. We propose a 2-arm randomized trial (RD vs. FTF) using intent-to-treat principles. Both arms will include individual monthly behavioral sessions (participant & caregiver), an eSLD, and increased PA. The RD arm will include group PA (2 session/wk.) delivered using video conferencing and will use commercially available web-based applications for self-monitoring and participant feedback for diet (Lose it!), PA (Fitbit activity tracker), and weight (wireless scales). The FTF arm will include a prescription for self-directed PA, and self-monitoring of diet and PA using paper/pencil self-reports modified for use with adults with IDD. The primary outcome (weight) will be assessed during home visits at baseline (mo. 0), following weight loss (6 mos.), during (12 mos.) and following maintenance (18 mos.) and after 6 mos. of no contact follow-up (24 mos.).

Table 1: Design Overview		INTERVENTION GROUPS
	Remote Delivery	Face-to-Face Delivery (FTF)
Behavioral sessions		
Delivery method	Individual video conferencing (Zoom on the iPad)	Individual FTF home visit
Meeting frequency /session duration		
Weight loss (0-6 mos.)	Monthly/45-60 min.	Monthly/45-60 min.
Maintenance (7-18 mos.)	Monthly/45-60 min	Monthly/45-60 min .
Diet	eSLD (portion controlled entrées and low kcal shakes + SLD)	eSLD (portion controlled entrées and low kcal shakes + SLD)
Supervised MVPA		
Delivery method	Group video conferencing (iPad mini) (10-12 participants)	NA
Session frequency /duration		
Weight loss (0-6 mos.)	2x/wk./30 min	NA
Maintenance (7-18 mos.)	2x/wk./30 min	NA

MVPA (supervised + unsupervised) (0-18 mos.)	150 min/wk.	150 min/wk.
Self-Monitoring (Diet)	Lose it! app	Self-report/pencil/paper
Self-Monitoring (PA)	Fitbit	Self-report/pencil/paper
Self-Monitoring (Weight)	Wireless scales	Portable scale-monthly FTF visit

eSLD=enhanced Stop Light diet; MVPA = Moderate-to-vigorous physical activity, NA = not applicable

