Participant eligibility. *Inclusion criteria:* 1) Age 18 yrs. and older (at least 50% female) with a diagnosis of mild to moderate IDD as determined by a Community Service Provider operating in Kansas under the auspices of a Community Developmental Disability Organization (CDDO). Participants will be judged competent to provide informed consent by their CDDO, or will have a guardian with power of attorney. Participants will not be enrolled without providing assent, regardless of guardian consent. 2) BMI ≥ 25 kg/m² and body weight ≤ 400 lbs. 3) Sufficient functional ability to understand directions, communicate preferences (e.g. foods), wants (e.g. more to eat/drink), and needs (e.g. assistance with food preparation) through spoken language. 4) Living at home with a parent/guardian, or in a supported living environment with a caregiver who assists with food shopping, meal planning, and meal preparation and agrees to serve as a study partner. 5) No plans to relocate outside the study area over the next 24 mos. 6) Internet access in the home. *Exclusion criteria.* 1) Unable to participate in MVPA. 2) Insulin dependent diabetes as this condition requires medical monitoring beyond the scope of this study. 3) Participation in a weight management program involving diet and PA in the past 6 mos. 4) Serious food allergies, consuming special diets (vegetarian, Atkins etc.), aversion to common foods (e.g., unwilling to consume dairy products, vegetables), diagnosis of Prader-Willi Syndrome. 5) Pregnancy during the previous 6 mos., currently lactating or planned pregnancy in the following 24 mos. Participants who become pregnant will be removed from the study and referred to appropriate agencies for consultation. 6) Serious medical risk, e.g., cancer, recent heart attack, stroke, angioplasty as determined by the PCP. 7) Unwilling to be randomized.

Withdrawal/Termination. The subject's participation will be terminated by the investigator if the diet does not appear to be in their best interest or if the subject becomes aggressive towards the study team. To withdraw from the study subject's guardian must contact the PI in writing. Once withdrawal has been received information will no longer be collected from them.

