Self-monitoring: All groups will monitor their daily diet and PA behaviors over the course of the 18 mo trial either by traditional pen and paper records or via iPad applications. Additional details regarding self-monitoring are described below.

Self-monitoring-RD group. Diet. Participants will log food/beverages (meals/snacks) using Lose it! by entering the food name and selecting the portion size, or by scanning the bar code of the food item using the iPad. A bar graph displays calories consumed compared with the goal providing immediate feedback (Appendix G). PA. Participants will wear a Fitbit Charge HR (size 35.5 x 28 mm) wireless

activity tracker on their wrist. The Fitbit records time spent in light, moderate or vigorous PA, based on step counts and heart rate (71). Data is automatically transferred to the Lose it! app via Bluetooth connectivity when the device is near the iPad, thus eliminating manual data recording. Lose it! provides immediate feedback on accumulated PA relative to participant goals via a graphic display. We successfully used the Fitbit in our adolescent IDD pilot trial (36). Body weight. Participants will self-weigh during monthly behavioral counseling video sessions using the wireless digital scale provided by the study which automatically syncs with the Lose it! app and updates a visual display of weight change. Reminders. Reminders will be sent via the Lose It! app if no information is reported for a given meal or goal (i.e., PA time). Diet/PA/weight data management. Diet and weight data on the Lose it! app are securely and automatically transferred to the Lose it! for Wellness Professionals web site that is accessible to the health educator. Fitbit data is automatically transferred to cloud storage (Fitabase, San Diego, CA). Diet and PA data will be accessible to health educators for use in behavioral sessions and will be exported to a data base for inclusion in exploratory analyses.

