Self-monitoring-FTF group. Diet/PA. Participants in the FTF group will be provided with a pedometer (Omron HJ-320, Lake Forest, IL) to self-monitor PA. The FTF group will enter diet (entrées, shakes, F/V) and PA data (type, duration, pedometer steps) on paper pictorial tracking sheets designed specifically for adults with IDD. Body weight will be assessed/recorded by the health educator on a calibrated scale during monthly home visits. Diet/PA data management. Diet/PA tracking sheets will be collected by health educators during monthly home visits and will be used as motivation, to inform participant counseling for the FTF group, and entered in a database for inclusion in exploratory analysis.

Incentives. Participants in both groups who complete self-monitoring for diet and PA on 5 of 7 d/wk. will be allowed to choose an iTunes song which will be uploaded weekly to the participant's iPad by study staff. Additionally, participants will receive a \$5.00 gift card for each behavioral session attended, \$20 for completing each of the 5 outcome assessments, and will be allowed to keep the iPad and Fitbit/pedometer on study completion (18 mos.). Study partners will receive gift cards (\$50.00) at 6, 12, and 18 mos. to compensate for the additional burden associated with participation in this trial.

Cost to Participants. All study cost will be paid for by the study including the iPad, fitbit, and exercise equipment. Participants and their families will not be charged if the participant loses any of the equipment, but must return them at the end of the study.

Intervention Deviations: As this study is intent-to-treat, all participants will be encouraged to follow the intervention described above, however they may choose not to follow the prescribed diet, track diet /PA, attend meetings, or weigh themselves. If a participant chooses not to follow the intervention as described, it will be recorded as process data and will not be considered an intervention deviation.

Assessments

Table 2: Assessment schedule					
Study Month	0	6	12	18	24
Outcomes: Primary/Secondary					
Weight/height/WC	X	X	X	X	X
Quality of life	X	X	X	X	X
Cost Analysis	→				

Demographics/health history	X			X	X
Outcomes: Exploratory					
Compliance-Diet/PA	X	X	X	X	
Behavioral session attendance					→
Self-Monitoring-Diet/PA					→
Study partner self-efficacy	X	X	X	X	
Medications	X	X	X	X	X

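### The primary-aim imputation is left to a data-dependent choice between two undefined methods, with five imputations the only number stated, the monthly weights unused and no missing-not-at-random analysis

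*Combined protocol and SAP*

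**What the plan says.** The Missing data paragraph of Statistical Methods is the whole plan for a missing month-6 weight. It commits to intent-to-treat with imputation and then sets two steps.

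- Step 1: "If the proportion of participants lost to follow-up differs by treatment we will determine if there are differences in demographic characteristics". The characteristics are sex, age and baseline weight, compared at p < 0.05. No test or threshold says when loss itself counts as differing.
- Step 2: "If missing data are related to treatment and/or demographic characteristics, we will use model based multiple imputation; otherwise, we will use traditional multiple imputation", the last with k=5. For neither form is there an imputation model, a variable list, a by-arm rule or a missingness assumption.

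Weights are also taken every month. In RD (Self-monitoring-RD group): "Participants will self-weigh during monthly behavioral counseling video sessions using the wireless digital scale". In FTF (Self-monitoring-FTF group): "Body weight will be assessed/recorded by the health educator on a calibrated scale during monthly home visits". The RD data-management text says: "Diet and PA data will be accessible to health educators for use in behavioral sessions and will be exported to a data base". The FTF text likewise names only diet and PA records for database entry. Under Intervention Deviations, participants are told that "they may choose not to follow the prescribed diet, track diet /PA, attend meetings, or weigh themselves".

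Scheduled outcome weights fall at months 0, 6, 12, 18 and 24 (Overview of approach, Table 2). On withdrawal: "Once withdrawal has been received information will no longer be collected from them".

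Elsewhere in the Analysis plan, Secondary aim 2 counts a missing weight as not reaching 5% loss, and Secondary aim 1 uses a linear mixed model. The only sensitivity analyses named are in Cost Analysis.

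**The concern.** Two statisticians following this paragraph could run different primary analyses. Read literally, the demographic comparison cannot change the branch. If loss differs by arm, missingness is already related to treatment and the *model based* branch applies. If loss does not differ, demographics are never examined. So a demographic pattern in balanced dropout goes unseen.

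Three further gaps bear on the non-inferiority decision. Five imputations leave visible random noise in the confidence limit that is compared with -3 kg. The monthly weights, which probably predict month-6 loss better than sex, age or baseline weight, are not planned for use. And nothing shows how far the primary conclusion depends on dropouts behaving like similar completers.

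**Working it through.** The documents give no SD, sample size, power or dropout rate for this trial, so there is no stated figure to reproduce.

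**Inputs from the documents:** two-sided 95% interval, margin -3 kg, equal allocation, k=5. The Analysis plan declares non-inferiority if the lower limit exceeds -3 and the upper limit exceeds 0.

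**Assumed base case:** 75 per arm, SD 5 kg, 20% missing in each arm.

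**Can the earlier trial fix the SD?** Under normality, 62.7% reaching 5% loss with a mean loss of 7.0% implies (7.0 - 5)/z(0.627) = 6.2%. With 67 analysed (one denominator that fits), the 95% interval for 62.7% is about 51–74%, which gives SDs from 3% to 71%. For 40.3% of 72 the interval (29–52%) includes 50%, so the SD has no upper bound. The SD therefore stays an assumption.

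**1. Seed noise**
- Complete-data variance of the difference: U = 2 × 25/75 = 0.667.
- With 20% missing and no predictor: T = 2 × 25/60 = 0.833, so the SE is 0.913 and the between-imputation variance is B = 0.833 - 0.667 = 0.167.
- Seed SD of the point estimate, √(B/k): 0.18 kg at k=5, 0.09 at k=20, 0.06 at k=50.
- The estimated SE also varies with the seed. That contribution is about 1.96 × (1 + 1/k) × B × √(2/(k - 1)) / (2√(U + (1 + 1/k)B)): 0.15, 0.06 and 0.04 kg.
- Combined in quadrature: 0.24, 0.11 and 0.07 kg. Simulation, which also lets the degrees of freedom vary, gives about 0.26, 0.12 and 0.07 kg.
- In simulation, two seeds disagree on non-inferiority in about 6–13% of trials at k=5 and 1–4% at k=50 (true difference 0 to -1 kg).

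**2. Power at a true difference of 0, random dropout (simulated)**

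| | Power |
|---|---|
| k=5, no interim weight | about 87–88% |
| k=5, one interim weight, correlation 0.5 to 0.8 with month-6 loss | about 89–92% |
| k=50, no interim weight | about 1–2 points above the first row |
| k=50, one interim weight, correlation 0.5 | about 1 point above the third row |
| k=50, one interim weight, correlation 0.8 | about 4 points above the third row |

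**3. False non-inferiority at a true difference of -3 kg**
- Hand formula: if RD dropouts truly lose δ kg less than imputed, the estimate shifts by 0.20 × δ, and the error is Φ(0.20δ/0.913 - 1.96). For δ = 3 kg the shift is 0.6 kg and the error is Φ(0.657 - 1.96) = 9.6%.
- Simulation with RD dropout logistic in early weight loss (log-odds 0.7–1.5 per SD, correlation of early with month-6 loss 0.5–0.8), k=5, interim weights unused: about 5–16%.
- The same mechanism in both arms: 2–3%. In FTF only: 0–2%, with lost power.

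**4. Does the upper-limit condition matter?** In the base case the interval is at least 2 × 1.96 × 0.913 = 3.58 kg wide. A lower limit above -3 then forces the upper limit above 0, so the 5–16% stands under both conditions. With 100 per arm, SD 4.5 kg and 30% missing, the SE is 4.5 × √(2/70) = 0.761 and the width 2.98 kg, so the second condition binds.

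**The case against.** The strongest reply is that this is a short specification gap dressed in large numbers. Several parts of it stand.

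- A reader might infer a post-hoc choice of method. The text does not support that. The rule is written in advance and looks at dropout and baseline characteristics, not at the treatment difference. It is data-dependent, and nothing shows that the check itself causes bias.
- A reader might infer that dropout will favour RD. The documents show no arm-specific mechanism. If poor responders left FTF instead, the bias would work against RD; shared or random dropout gives none.
- A reader might stretch the inputs and the lower-limit test alone to an error near one third. With 100 per arm and SD 4.5 kg, adding the plan's upper-limit condition cuts the error from 32% to 25% at 30% missing, and from 4–5% to 1.3% at 10% missing. Over wider inputs the result depends on the assumed SD, so no general range is claimed.
- The efficiency loss from k=5 is small. Relative efficiency 1/(1 + FMI/5) is 0.98 to 0.94 for a fraction of missing information (FMI) of 0.1 to 0.3.
- The simulated gain uses one clean interim weight. The real ones are up to six correlated, intermittently missing values, self-measured in RD and measured by the educator in FTF.
- Secondary aim 2 does treat missing weight as failure, and Secondary aim 1 is a partial cross-check under missing at random. Neither closes the gap. The first concerns a proportion, not the primary mean difference. The second has only the baseline weight for someone who never returns.

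What remains is textual: undefined methods, one stated k on one branch, recorded weights left out, and no missing-not-at-random analysis of the primary difference.

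**Conclusion.** The point holds as a specification gap with a cheap, better alternative, and should be addressed. It rests on the text; the figures only show its scale under the assumed base case. There, seed noise in the deciding limit is about 0.26 kg at k=5, more imputations recover about 1–2 points of power, and one interim weight adds roughly 1–5 points depending on its correlation with month-6 loss. The 5–16% false non-inferiority is conditional on response-driven dropout in RD only. The documents neither establish nor exclude that, which is the reason to plan a sensitivity analysis rather than to predict bias. Confidence is medium, because trial size, SD and dropout are all assumed.

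**What to change.** Remove the dropout check as a way of choosing the method, and pre-specify:

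1. One MI model, run separately by arm, with baseline weight, sex, age and all available monthly and scheduled weights up to month 6. Name a reduced set in advance, such as the last available monthly weight, in case the full set is unstable. Allow for household if clustering is found.
2. A fixed seed and a fixed number of imputations: at least 20, preferably 50.
3. A tipping-point analysis. Reduce the imputed RD losses in fixed steps until the lower limit reaches -3 kg, and report that delta. It is about (lower limit + 3)/(RD missing share). A lower limit of -2.5 kg tips at about 0.5/0.10 = 5.0 kg, 0.5/0.20 = 2.5 kg or 0.5/0.30 = 1.7 kg. If the lower limit is already at or below -3 kg, there is nothing to tip.

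The cost is SAP wording, modest programming and some data handling. Monthly weights must be added to the analysis database: up to six per person, so 300–600 FTF values at an assumed 50–100 per arm. RD weights already sync electronically.

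The downside is data quality. The weights are measured differently by arm, are optional for participants and will be sparse for early leavers. Under the COVID 19 section, face-to-face contact moves to phone and assessment materials go to homes, so weights from that period may be missing or measured differently and need a flag. Monthly weights can reduce bias without removing it, which is why item 3 is needed as well.
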